6.3 Minimization of Anticipated Risks

Potential risks that may be associated with use of VeraCept have been minimized in this study by the following:

- Establishing eligibility criteria that exclude subjects who are at higher risk for experiencing an anticipated AE;
- Conducting extensive preclinical and clinical testing prior to the start of this Phase 3 clinical study;
- Conducting a risk analysis and incorporating mitigations to eliminate and/or reduce risks to as low as possible in accordance with ISO 14971-Medical Devices Application of risk analysis to medical devices;
- Manufacture of VeraCept per Good Manufacturing Practice (GMP) guidelines;
- Selecting investigators with proper level of training and experience in placing IUSs;
- Ensuring adequate monitoring is performed to identify any safety issues associated with the study procedure and subjects;
- Regularly reviewing reported SAEs and AEs throughout the study and taking appropriate medical measures to resolve the adverse events;
- Utilizing a data and safety monitoring board (DSMB) to oversee safety and performance outcomes.
- Providing adequate study oversight to ensure compliance with GCP.

6.4 Safety Review

The Medical Monitor will evaluate safety and pregnancies on an ongoing basis and significant findings will be addressed immediately. A monthly safety and pregnancy review will occur with the study principal investigator to review safety trends, including pregnancies. The medical monitor, the responsible project team, and sponsor personnel will review study drug-related findings periodically. Additional details are located in the Medical Monitoring Plan. If the medical monitor identifies any safety issues that may alter the risk benefit ratio of the study product, the medical monitor will immediately inform the project team and the sponsor.

The study will utilize a DSMB to oversee safety and performance outcomes. The DSMB charter will include stopping criteria in the event an unacceptable rate of pregnancy is observed. The stopping criteria will be assessed by observing the lower bound of the 95% confidence interval of the cumulative pregnancy percentage (Kaplan-Meier) at the given timepoint (e.g., cycle 6) for the VeraCept treatment. If the lower bound of the 95% confidence interval is greater than the decision point for the given DSMB meeting, then the DSMB will recommend suspension of enrollment into the study until a thorough review of risks and benefits can be performed since subjects appear to be at a higher risk of pregnancy than expected. The decision point used for each DSMB meeting will depend upon how much data is expected to be available at the timepoint of interest (e.g., cycle 6) for the DSMB meeting. The timepoint used for the Kaplan-Meier analysis and the decision point for each DSMB meeting will be specified in the DSMB charter. The DSMB charter will detail the number and timing of DSMB reviews. The sponsor can request additional DSMB meetings if they have any concerns.

7 SELECTION AND TRAINING OF CLINICAL SITES AND INVESTIGATORS

The study will be conducted at approximately 45 centers in the US:

- Experience and adequate training in IUS use and conduct of regulated clinical studies
- Adequate facilities and equipment
- Adequate patient volume
- Appropriate personnel and site research staff to support the conduct of the study, and
- Commitment to safety and adherence to the investigational plan

Prior to acceptance of the site into this study, the sponsor or its designee will conduct a site qualification visit (if applicable). The site qualification visit will be scheduled to include time with the principal investigator, co-investigators, study coordinator, and other study personnel as available. Areas of discussion include a review of personnel training, expertise, and FDA-regulated study experience, this study's specific requirements, and a review of staffing and equipment availability and appropriateness.

Prior to study implementation, the study monitor will ensure that study personnel:

 Have appropriate training, facilities, time, and willingness to comply fully with the study requirements.

- A central Investigational Review Board (IRB) will be used to review and approve the
 Investigational Plan wherever possible, but if it is not possible, the investigator will
 submit this Investigational Plan to the local IRB for appropriate review and obtain
 written approval for the conduct of the study prior to the initiation of any subject
 enrollment into this study.
- Maintain all study correspondence, this Investigational Plan, and all related and required records on file at their facility.
- Assume full responsibility for the study investigation at their individual medical
 practices, clinics, and medical facilities. The study monitor will create a written report
 of the pre-study site visit. Resolution of any concerns and/or completion of any
 appropriate study activities identified during the pre-study visit will be documented
 by the study monitor, discussed with the sponsor and submitted to the investigator.
- Complete any training required by the IRB regarding protection of human subjects.
- Complete training on use of the eCRFs provided by Sebela representative or designee.
- Review and are familiar with VeraCept Clinician's Quick Guide and Investigator Brochure.
- Complete training with VeraCept, provided by a Sebela representative or designee.

Throughout the conduct of the study, the sponsor and/or its designees will closely monitor each site for the following:

- Compliance with the investigational plan
- Meeting enrollment commitments
- Accurate and timely submission of CRFs and additional data
- Compliance with International Conference of Harmonization (ICH) E6 Good Clinical Practice (GCP) guidelines
- Compliance with the Declaration of Helsinki
- Compliance with IRB and local regulatory requirements

7.1 Laboratories

Local laboratories will be used for all lab tests performed. No central labs will be used in this study.

8 STUDY POPULATION

The study population will be post-menarcheal, pre-menopausal women up to 45 years of age, who are at risk for pregnancy and who desire a long-term intrauterine contraceptive for birth control. Both parous and nulliparous women are eligible.

Subjects must provide written informed consent and assent, if applicable, and meet the study entry criteria noted below.

8.1 Inclusion Criteria

Subjects must meet all of the following criteria to participate in this study:

- 1. Post-menarcheal, pre-menopausal females up to 45 years of age at the time of informed consent/assent and in good general health;
- 2. History of regular menstrual cycles defined as occurring every 21-35 days when not using hormones or prior to recent pregnancy or spontaneous or induced abortion;
- 3. Sexually active with a male partner who has not had a vasectomy;
- 4. Reasonably expect to have coitus at least once monthly during the study period;
- 5. In a mutually monogamous relationship of at least 3 months duration;
- 6. Seeking to avoid pregnancy for the duration of the study;
- 7. Willing to use the study drug as the sole form of contraception;
- 8. Willing to accept a risk of pregnancy;
- 9. Subjects must be in compliance with cervical cancer screening guidelines per the American Society for Colposcopy and Cervical Pathology (ASCCP) guidelines without evidence of disease. Subjects who are age 21-24 y/o, at time of informed consent, must have a normal Papanicolaou test (Pap), atypical squamous cells of undetermined significance (ASC-US), or low-grade squamous intraepithelial lesion (LSIL). Subjects who are 25 or older at the time of informed consent with ASC-US results, must also have a negative high-risk human papilloma virus (HPV) test result within the appropriate screen timeframe, and prior to study IUS insertion. Alternatively, the subject must have had a colposcopy performed within the appropriate screen timeframe per American Society for Colposcopy and Cervical Pathology (ASCCP) guidelines, and prior to study IUS insertion that showed no evidence of dysplasia requiring treatment per ASCCP guidelines, or treatment was performed and follow-up at least 6 months after the treatment showed no evidence of disease by clinical evaluation;
- 10. Able and willing to comply with all study tests, procedures, assessment tools (including e-diary), and follow-up;
- 11. Able and willing to provide and document informed consent and Authorization for Release of Protected Health Information (PHI). Unemancipated subjects under 18 years old must provide assent and have written parental consent documented on the consent form consistent with local legal requirements;
- 12. Plan to reside within a reasonable driving distance of a research site for the duration of the study;
- 13. Subject agrees not to self-remove VeraCept;

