11 STUDY SCHEDULE OF ASSESSMENTS

A schedule of assessments for all VeraCept subjects is provided in Table 1.

Table 1: Study Schedule of Assessments

| | | Screen | | | Years 1-8 | | | 0 | ther |
|---|---|-----------|--|---|---|--|--------------------------------|---|---|
| | | Screening | Enrollment (VeraCept Placement) Day 1 | Office Visits: W 6 ± 1 w W 13 ± 1w W 26 ± 2w W 52 ± 2w | Regular Contact ⁹ : W 17, 21, 30, 34, 39, 43, 47 ±1w Monthly M13- 17, M19-23, M25-29, M31-35 (±1 w) | Office Visits: M 18, 24, 30, 36, 42, 48, 54, 60, 66, 72, 78, 84, 90 (± 1 m) | M 96 + 1 m or Exit Visit | Contact to confirm pregnancy for those desiring pregnancy ⁸ | 30-Day Post- Removal AE follow-up |
| | Assessment of Eligibility | X | X | | | | | | |
| / tics | Distribution of subject materials, if applicable | X | | | | | | | |
| Initiation/ Subject Characteristics | Informed consent and assent, if applicable, PHI and Bill of Rights forms (where applicable) | X | | | | | | | |
| Init Su sara | Demographics and baseline characteristics | X | | | | | | | |
| C | Med/surgical, gynecological and menstrual history | X | | | | | | | |
| | Vital signs and weight | X | X | X | | X | X | | |
| | Height | X | | | | | | | |
| | General physical exam | X | | | | | X | | |
| od v | Pelvic exam (string check if post IUS insertion) | X | X^1 | X^1 | | X^1 | X^1 | | |
| Safety and Efficacy | Cervical cytology | X | | | | | | | |
| ıfet | Cervical infection tests | $X^{5,7}$ | | | | | | | |
| SS | Transvaginal ultrasound ² | | X^2 | X^2 | | X^2 | X^2 | | |
| | Pregnancy test-urine | X | X | X | | X | X^4 | | |
| | Prior and concurrent medication | X | X | X | X | X | X | | |
| | Adverse events | | X | X | X | X | X | | X^{16} |
| | Contact IWRS | X^{12} | X^{13} | | | | X | | |
| | IUD placement | | X | | | | | | |
| | IUD placement ease | | X | | | | | | |
| | IUD placement pain (11-point scale) | | X^{10} | | | | 7 714 15 | | |
| ı | IUD removal | | | | | | X ^{14,15} | | |
| Other | IUD removal ease | | | | | | X X ¹¹ | | |
| 0 | IUD removal pain (11-point scale) Concomitant contraception | | X | X | X | X | X ¹⁴ | | |
| | Subject education - need for contraception | X | X | X | X | X | X | | |
| | Subject education - need for contraception Subject e-Diary training and re-training | X^{3a} | X | X | X | X | Λ | | |
| | e-Diary reviewed with subject ⁶ | Λ | X^{3a} | X^{3b} | X ^{3b} | X^{3b} | X^{3b} | | |
| | Discontinued Subject Desiring Pregnancy | | 21 | 71 | 21 | 21 | | X8 | |

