- Counsel the subject that if at any time, she believes the study drug may have been expelled or is no longer in place, the subject should call immediately for an urgent study visit and refrain from having sex or use appropriate non-hormonal contraception until further evaluation is completed. (See Section 4.5 for details)
- E-diary review with subject:
 - Review for completeness. If not complete, subject to enter information, if within 7- day open timeframe. Remind the subject to complete diary contemporaneously.
 - o Verify sexual activity and if any back-up contraception method is documented
 - o Review subject's diary and assess for adverse events
 - o Re-education on e-diary completion, if needed
 - o Subject recorded adverse events
 - Subject recorded interval and concurrent medications

12.6 Office Visits: Months 18, 24, 30, 36, 42, 48, 54, 60, 66, 72, 78, 84, 90 ±1Month from VeraCept Insertion

Starting at Month 18 from VeraCept insertion the subject will return for follow-up visits every 6 months through Month 90 (Year 8). At these follow-up visits, the following will be performed:

- Vital signs and weight
- Type(s) of menstrual products subject has used since the last visit
- Pelvic exam (string check)
- Transvaginal ultrasound to document VeraCept position, if clinically indicated
- Urine pregnancy test
- Interval and concurrent medications
- Adverse events
- Use of concomitant contraception;
- Counsel the subject that if at any time, she believes the study drug may have been expelled or is no longer in place, the subject should call immediately for an urgent

study visit and refrain from having sex or use appropriate non-hormonal contraception until further evaluation is completed. (See Section 4.5 for details)

- E-diary review with subject:
 - Review for completeness. If not complete, subject to enter information, if within 7- day open timeframe. Remind the subject to complete diary contemporaneously.
 - Verify sexual activity and if any back-up method is documented
 - o Review subject's diary and assess for adverse events
 - o Re-education on e-diary completion, if needed.
 - Subject recorded adverse events
 - Subject recorded interval and concurrent medications

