12.12.2 Lost to Follow-Up

A lost to follow-up subject is a subject who does not come in for an exit visit/VeraCept removal at the time of study completion and their final status outcome is unknown. Study completion is defined as Month 60 (Year 5) for subjects who did not consent to the extension study and Month 96 (Year 8) for those who did consent to the extension study.

Subjects not returning for an exit visit but who provide a final status are not considered lost to follow-up (e.g., device removed by outside provider, withdrew consent, refused VeraCept removal, etc.). Every effort should be made to retrieve VeraCept for final study drug disposition.

Subjects previously designated as lost to follow-up under the prior lost to follow-up guidance (protocol Amendment version 6.0 or earlier) will be required to be contacted annually until the visit window for Month 60 (Year 5) has closed. Refer to Study Reference Manual for additional instructions.

Subjects discontinued as lost to follow-up who later resume contact with the site should be requested to come in for device removal or confirmation of removal and with a request to return VeraCept, if possible (see CCGs for instructions on updating the CRFs).

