13 E-DIARIES

Subjects will be instructed to complete e-diaries daily. Training and detailed instructions on how to complete the e-diary will be provided to subjects. The screening period will be used to train the subjects on how to use the e-diary and to assess the subject's e-diary completion compliance. The diary data collected during the screening period will not be used in the analysis. Subjects will have up to 7 days to input e-diary data for each day. During subject visits and contacts, the site should review the e-diary with the subject to assess for e-diary completion. In addition, all e-diary entries should be reviewed and assessed for adverse

events and concomitant medications. Subjects should be re-educated if they are not completing the diary or are incorrectly completing it. E-diaries are designed to collect the following information for each day of the 28-day cycle from Screening through Month 12:

- Day of cycle
- Date
- Absence or presence of scheduled (menstrual) or unscheduled (intermenstrual)
 vaginal bleeding/spotting (none, spotting, light bleeding, normal bleeding or heavy
 bleeding)
- Vaginal intercourse
- IUD expulsion (yes, no, suspected)
- Usage of additional birth control methods and type of birth control used
- Presence of menstrual pain or cramping
- Adverse events
- Concomitant medications

Vaginal bleeding categories are defined as follows:

- None: no bleeding or spotting
- Spotting: a minimal amount of vaginal bleeding and only one panty liner is used all day or did not use any protection (panty liner, pad, tampon)
- Light bleeding: have vaginal bleeding and one or two pads or tampons are used, or more than one panty liner is used, throughout the day
- Medium bleeding: have vaginal bleeding and three or four pads or tampons are used throughout the day
- Heavy bleeding: have a large amount of vaginal bleeding and more than four pads or tampons are used throughout the day

From Month 13 – Month 96 the following will be collected:

- Day of cycle
- Date
- Vaginal intercourse
- IUD expulsion (yes, no, suspected)
- Usage of additional birth control methods and type of birth control used
- Adverse events
- Concomitant medications

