20.6 Primary Endpoint Analysis

The primary efficacy endpoint in the study is contraceptive efficacy through three years of use and will be analyzed using the Pearl Index with 95% confidence interval for women in the EP population. Cycles (defined as 28 days) during which no intercourse occurs, or backup methods of contraception (including emergency contraception) are used will be excluded from the primary analysis of the Pearl Index unless the subject had an on-treatment pregnancy in that cycle. If Cycle 1 is evaluable, it will be included in the analysis regardless of the timing of VeraCept insertion relative to the subject's last pre-insertion menses.

One year is defined as comprising thirteen 28-day cycles.

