20.9 Determination of Sample Size

Approximately 1,605 subjects will be enrolled on an open label basis. It is planned that 1,480 of the 1,605 VeraCept subjects will be in the up to 35-year age range and the remaining 125 subjects will be in the 36 to 45-year age range. It is expected that at least 40% of enrolled subjects will be nulliparous.

It is expected that 1,480 post-menarcheal VeraCept subjects up to age 35 years will provide at least 620 women with at least 3 years of use of VeraCept. It is expected that the study will have 577 woman-years of use in Year 3 of the study who are evaluable for the Pearl Index analysis. This will allow for the Pearl Index calculation for Years 1, 2, and 3 of the study and for the cumulative 3 years to have an upper bound of the 95% confidence interval no more than 1 unit above the point estimate of the Pearl Index.

It is also expected that 1,480 post-menarcheal VeraCept subjects up to age 35 years will provide at least 350 women with 5 years of use of VeraCept.

The 1,605 enrolled VeraCept subjects are expected to provide over 17,000 cycles (28-day cycles) of exposure in Year 1. Over 54,000 VeraCept cycles are expected to be collected during the course of the 5-year study.

The 1,605 enrolled VeraCept subjects are expected to provide at least 200 women with 8 years of use of VeraCept. Over 65,000 VeraCept cycles are expected to be collected during the course of the 8-year study. These 8-year projections assume that 10% of the subjects that complete 5-years of use will not consent to extending their use of VeraCept beyond Year 5.

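### After Day 1 no one re-checks partner vasectomy or subject sterilisation, and neither is defined as a backup method, so cycles not at risk of pregnancy can stay in the Pearl Index denominator

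*Protocol*

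**What the plan says.** **Entry.** Protocol 8.1, criterion 3, requires the subject to be "Sexually active with a male partner who has not had a vasectomy". In Table 1 (protocol section 11) the eligibility row reads "Assessment of Eligibility | X | X": it is marked at Screening and Day 1, and every later column is blank.

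**Extension.** Going beyond Month 60 is described only in terms of consent. Protocol 12.12.2 states that "Study completion is defined as Month 60 (Year 5) for subjects who did not consent to the extension study". Protocol 20.9 assumes that "10% of the subjects that complete 5-years of use will not consent to extending their use of VeraCept beyond Year 5". No re-check of entry criteria is described at that point.

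**Follow-up data.** The e-diary (protocol section 13) collects "Usage of additional birth control methods and type of birth control used" through Month 96. At the Month 18 to 90 office visits (protocol 12.6) sites review concomitant contraception and are told to "Verify sexual activity and if any back-up method is documented".

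**Analysis.** Protocol 20.6 states: "Cycles (defined as 28 days) during which no intercourse occurs, or backup methods of contraception (including emergency contraception) are used will be excluded". The exception is a cycle with an on-treatment pregnancy. SAP 4.1.5 takes backup use and intercourse from the subject's diary, treats a missing backup entry as no backup use, and treats a missing intercourse entry as no intercourse. SAP 4.1.6 and 4.9 also exclude cycles with no diary data. Neither document defines a backup method.

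**The concern.** Criterion 3 keeps out women whose exposure would say nothing about the device. The same situation can arise later. Follow-up lasts up to 8 years, entry requires a relationship of only 3 months, and women in the EP population may be up to 35 at enrolment and so up to 43 at the end. A partner may have a vasectomy, the partner may change, or the subject may be sterilised.

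Nothing is used on a given day after a vasectomy or sterilisation, so a daily question about use of additional methods may well be answered no or left blank. Cycles of this kind that are counted add to E (evaluable cycles) and almost never add to x (pregnancies). The Pearl Index and both confidence limits are then too low. The 3-year Pearl Index is the primary endpoint, and protocol section 20 says data up to 8 years will be assessed for further filings on longer use.

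**Working it through.** **1. How one woman is counted.** Suppose a partner has a vasectomy, and over the next thirteen 28-day cycles the woman records intercourse in each. SAP 4.1.5 sets NCYCEV = NCYCR - NCYCEXCL.

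- No additional method recorded, or entry blank: NCYCEXCL gains 0, so E gains 13 cycles (one woman-year).
- Vasectomy recorded as a method, and classed as backup by the analyst: NCYCEXCL gains 13, so E gains 0.

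The same woman contributes 13 cycles or none, depending on what she enters and on a classification that neither document makes. The main life table inherits this, because CYCLENAC = CYCLEN - NCYCEXCL. The planned sensitivity analysis (CYCLEN) removes no cycles, so it does not address the question.

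**2. The plan's own figure.** Protocol 20.9 expects 577 evaluable woman-years in Year 3 and an upper 95% bound no more than 1 unit above the point estimate. With the exact Poisson interval of SAP 4.9, the woman-years needed are

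100 × (½ χ²(0.975, 2(x+1)) - x).

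| x | Woman-years needed | Share of 577 that could be removed |
|---|---|---|
| 0 | 368.9 | 36.1% |
| 1 | 457.2 | 20.8% |
| 2 | 522.5 | 9.5% |
| 3 | 576.7 | 0% |
| 4 | 624.2 | target already missed |

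The last column is 1 - needed/577. So 577 is reproduced at x = 3 (Pearl Index 0.52, upper bound 1.519, gap 0.999). The documents do not state x = 3; it is the count that returns their figure.

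**3. Direction and size of the bias.** Reported Pearl Index = 1300x/E. If a share f of E is not at risk, the at-risk Pearl Index = 1300x/(E(1-f)). The ratio 1/(1-f) applies to the point estimate and to both limits.

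**4. Exposure in Years 6-8.** From protocol 20.9, (65,000 - 54,000)/13 = about 846 woman-years, all ages, before cycle exclusions. Both cycle totals are stated as minimums, so the difference is approximate. Pro-rating to women up to 35 (an assumption) gives 846 × 1,480/1,605 = about 780.

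**5. Illustration.** The values of f and the pregnancy counts are assumptions; the documents give neither.

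| f | 1/(1-f) | Year 3, x = 2, 577 woman-years: at-risk PI (upper), gap | Years 6-8, x = 4, 780 woman-years: at-risk PI (upper) |
|---|---|---|---|
| 0% | 1.00 | 0.347 (1.252), 0.905 | 0.513 (1.313) |
| 2% | 1.02 | 0.354 (1.278), 0.924 | 0.523 (1.339) |
| 5% | 1.05 | 0.365 (1.318), 0.953 | 0.540 (1.382) |
| 10% | 1.11 | 0.385 (1.391), 1.006 | 0.570 (1.458) |
| 15% | 1.18 | 0.408 (1.473), 1.065 | 0.603 (1.544) |

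The row f = 0% is what would be reported if nothing were removed.

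**The case against.** The strongest reply is that existing controls already cover this. The introductions of both documents list tubal ligation and partner vasectomy among contraceptive options. Inclusion 7 requires willingness to use the device as the only method, and protocol 14.1 bars other birth control that could affect the results. The diary asks for the type of any additional method through Month 96. Table 1 has a concomitant-contraception row at office visits, contacts and exit. Cycles with backup are excluded, and major violations that materially affect the primary efficacy assessment remove a subject from the EP population. The missing-data rules also work in the other direction: cycles with no recorded intercourse or no diary data drop out.

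Much of this stands. A reader might infer that all such exposure necessarily stays in the denominator. The documents do not support that: a woman who records the vasectomy, and whose entry is classed as backup, has those cycles removed. The diary's response list, the eCRF pages and the reference manual are not available here, so it is unknown whether vasectomy or sterilisation is an offered answer.

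What does not stand is that the gap is closed. Listing vasectomy in an introduction is not an analysis rule. The SAP names the diary as its source for backup use, not the visit review of concomitant contraception, and no date of vasectomy or sterilisation is required anywhere. The EP exclusion acts on whole subjects at the sponsor's discretion, not on dated cycles.

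**Conclusion.** The gap is real but conditional. Cycles not at risk can stay in the Pearl Index denominator when the vasectomy or sterilisation goes unrecorded or is not classed as backup. The bias is then downward, by the factor (1-f) on the estimate and both limits. The value of f cannot be derived from the documents. At 2%, 5% and 10% the at-risk Pearl Index is 1.02, 1.05 and 1.11 times the reported one.

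Two further inferences go too far. One is that the fault belongs to the Year 5 extension. It runs from Day 1 and reaches the 3-year primary endpoint; the extension is a missed chance to re-check, and the Year 4 to 8 analyses are secondary and descriptive. Accumulation into Years 6-8 is plausible because such events add up over time, but no figure in the documents measures it. The other is that criterion 3 alone defines being at risk of pregnancy. It is one of several criteria behind that phrase.

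The change should be made: without a dated record no at-risk filter can be applied, and the error favours the product.

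**What to change.** **Data.** At extension consent and at each existing six-monthly office visit, add one eCRF item: start and stop dates of any period in which the current partner is vasectomised or the subject is sterilised. Ask once retrospectively for elapsed time. This reaches only women still in follow-up and depends on recall.

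**Rule.** State in protocol 20.6 and SAP 4.1.5 that these periods count as backup contraception. Put cycles within the dates in NCYCEXCL unless an on-treatment pregnancy occurs in the cycle; CYCLENAC then follows by compression. Treat a cycle that straddles a date as the plan treats any cycle with some backup use. The stop date matters: a woman who later has a non-vasectomised partner is at risk again, and excluding her cycles indefinitely would bias the Pearl Index upward.

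**Reporting.** Add a sensitivity analysis of the Pearl Index and life table with these cycles included. Keep the women in all safety, expulsion and continuation analyses.

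**Cost.** One question at visits that already review contraception, and one derivation line. The SAP follows protocol version 3.0 and stops at Year 5, so Years 6-8 need a derivation in any case. Evaluable cycles fall slightly and the Pearl Index becomes slightly less favourable. With three pregnancies in Year 3 the precision target has no slack, so any material exclusion would miss it, but cycles not at risk add no real information towards that target.
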